Eligibility for participation in the study will be based on the inclusion/exclusion criteria. Specifically, candidates must meet all entry criteria at Screening or at the time point specified in the individual eligibility criteria listed in the protocol.

Prospective approval of protocol deviations to recruitment and enrollment criteria, also known as protocol waivers or exemptions, is not permitted.

C. Sample Size Predictions

The intent of the primary efficacy analysis is to demonstrate superiority of at least 1 therapeutic dose of PCN-101 Solution for Injection (30 mg or 60 mg) versus placebo based on the change in the MADRS total score from predose to 24 hours postdose.

For the primary analysis, a sample size of 93 randomized subjects (31:31:31) will provide 80% power to detect an 8-point difference between each PCN-101 Solution for Injection dose and placebo in the mean change from baseline MADRS total score at 24 hours postdose, using a t-test with $\alpha = 0.05$ (2 tailed) and assuming a common standard deviation (SD) of 11.

Approximately 20 study centers in the EU and US are expected to participate in this study. The enrollment of 93 subjects is planned. Subjects who do not receive a dose of study treatment on Day 1 (Visit 2) will be replaced.

D. Treatment Randomization

Two doses (30 mg and 60 mg) of IV PCN-101 will be compared with placebo to determine the most effective dose in improving depressive symptoms in subjects with TRD.

Randomization will be used to minimize the bias in the assignment of subjects to treatment arms and to increase the likelihood that known and unknown subject characteristics are evenly balanced across treatment arms. Randomization will be stratified by region (US, EU). This will improve the validity of the statistical comparisons among treatment arms across different geographical regions. Blinded treatment will be used to reduce any potential bias during the collection of data and the analysis of clinical endpoints.

E. Assessment Schedule

The various assessments that will be conducted during this study are summarized in the protocol.

IV. Interventions

A. Clinical Trial Material

The investigational medical products are PCN-101 (30 mg and 60 mg) and Placebo.

V. General Analytical Considerations

A. Data Sources

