Within a single analysis timepoint per patient, if $\geq 25\%$ of items used to calculate a total score for a given scale are missing, the total scale score for that patient and timepoint will be considered missing.

If $<25\%$ of items are missing, the total score will be calculated (prorated) as the arithmetic mean of non-missing items multiplied by the total expected number of items and rounded up to the nearest integer.

Additionally, separate sensitivity analyses will be performed with missing MADRS data imputed with a multiple imputation method. The multiple imputation (MI) method assumes a missing-at-random (MAR) data missing pattern. Imputation will be performed using the Fully Conditional Specifications parametric regression model. A total of 50 imputations will be generated using PROC MI. For each of the 50 datasets, missing MADRS total score will be imputed using the regression model, as implemented in the PROC MI with the following variables considered (as given on the VAR statement): Treatment, Region, Baseline MADRS and each subsequent post-baseline MADRS score. Response status (Yes, No) and revised change from baseline values will be derived in each MI dataset based on the newly imputed data. The seed to be used in this MI model is 60773.

Example SAS code for PROC MI is as follows:

```
PROC MI DATA=MI NIMPUTE=50 SEED=&SEED. OUT=MI1 ROUND=1 MINIMUM=0;
  CLASS TRTP REGION1;
  VAR TRTP REGION1 ATPTN20 ATPTN40 ATPTN50 ATPTN70 ATPTN80
  ATPTN90;
  FCS REG (ATPTN20 = TRTP REGION1);
```

```
FCS REG (ATPTN40 = TRTP REGION1 ATPTN20) ;
FCS REG (ATPTN50 = TRTP REGION1 ATPTN20 ATPTN40 ) ;
FCS REG (ATPTN70 = TRTP REGION1 ATPTN20 ATPTN40 ATPTN50) ;
FCS REG (ATPTN80 = TRTP REGION1 ATPTN20 ATPTN40 ATPTN50
ATPTN70 ) ;
FCS REG (ATPTN90 = TRTP REGION1 ATPTN20 ATPTN40 ATPTN50
ATPTN70 ATPTN80) ;
RUN;
```

Note: TRTP = randomized treatment group, REGION1 = region (US/Europe). Note: Each of the ATPTNxx variables represent the MADRS score at each analysis timepoint (Pre-dose, 2 hours, 4 hours, 24 hours, Day 8 and Day 15).

The imputation models may be modified based on the actual data if there is an issue in model convergence. If the missingness at the MADRS 24 hour timepoint is >5%, additional analyses exploring missing-not-at-random (MNAR) assumptions will be performed.

F. Primary Efficacy Outcome Analysis

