Sensitivity analyses reviewing missing data assumptions will be performed using the same MMRM model specifications as described in [Section VII.F Primary Efficacy Outcome Analysis](#). One analysis will be performed for only the data collected from subjects who were treatment compliant and a separate analysis will be performed with those who completed the study.

In addition, sensitivity analysis exploring the MAR assumptions with multiple imputation of MADRS related endpoints will be performed as described in [Section VII.E Handling of Missing Item Efficacy Endpoint](#). Analysis of each primary and secondary MADRS endpoints will be performed for each of the MI datasets. The analyzed results from the 50 imputed datasets will be combined based on Rubin's rules (Rubin, 1987) using PROC MIANAYLZE in SAS to estimate the pooled analysis results.

H. Secondary Efficacy Analyses

Change from baseline in MADRS total score

Summaries of actual values and changes from baseline score will be presented by treatment group for all analysis timepoints (including 24 hours after start of infusion), beginning with the Baseline visit for the FAS.

Proportion of subjects with $\geq 50\%$ improvement in MADRS total score

For the responder analysis based on a $\geq 50\%$ improvement in MADRS total score at each analysis visit, the proportion of responders will be calculated using frequency counts and percentages, presented for each treatment group.

The response rate between each PCN-101 dose versus Placebo at each analysis visit will be compared using a logistic regression using fixed effects of treatment group, analysis visit, region and treatment group-by-visit interaction. The baseline value will be included as a covariate. Odds ratios (ORs), corresponding two-sided 95% CI and p--values will be derived.

Proportion of subjects with a MADRS total score ≤ 10

The same analysis will be performed as described for the endpoint of proportion of subjects with $\geq 50\%$ improvement in MADRS total score.

Change from baseline in QIDS-SR-16, GAD-7 and EQ-5D-3L

The MMRM model with the same specification as detailed in Change from baseline in MADRS total score will be used to analyze the following secondary efficacy measures for the FAS. Missing data will not be imputed.

- Change from baseline in QIDS-SR-16 by visit
- Change from baseline in GAD-7 by visit
- Change from baseline in EQ-5D-3L VAS by visit

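### The example imputation code predicts a missing 24-hour MADRS score from earlier visits only, although SAP VII.E describes fully conditional imputation and the primary MMRM uses all visits (minor)

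*SAP*

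**What the plan says.** SAP VII.E sets out the method in words: "Imputation will be performed using the Fully Conditional Specifications parametric regression model". It then names the variables to be considered, which are those on the VAR statement: "Treatment, Region, Baseline MADRS and each subsequent post-baseline MADRS score". The VAR statement in the example code does list all six MADRS timepoints.

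The FCS statements that follow give each timepoint its own predictor list. For the 24-hour score the list is "FCS REG (ATPTN70 = TRTP REGION1 ATPTN20 ATPTN40 ATPTN50", that is, treatment, region, predose, 2 hours and 4 hours. Day 8 (ATPTN80) and Day 15 (ATPTN90) are absent. The variable names are matched to visits by their order in the note under the code. The other five models follow the same pattern, so Day 8 is imputed without Day 15.

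SAP VII.G gives the purpose: "sensitivity analysis exploring the MAR assumptions with multiple imputation of MADRS related endpoints will be performed". The 50 completed datasets feed the primary and secondary MADRS endpoints, pooled by Rubin's rules. The primary MMRM in SAP VII.F is fitted over all analysis visits with an unstructured covariance and no imputation.

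**The concern.** In the primary MMRM, a subject who lacks a 24-hour score but has a Day 8 score still contributes to the 24-hour estimate through the covariance between visits. In the coded imputation, the same subject's 24-hour score is drawn as if Day 8 had never been observed. The imputation therefore needs a narrower assumption than the model it is meant to check: that missingness at 24 hours is unrelated to later scores once the earlier ones are known.

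If the two analyses differ, the reader cannot tell whether the cause is the missing data or the predictor list. The imputed values are also less precise than the observed data allow.

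The pattern can arise in this trial. Under SAP VII.E a MADRS total becomes missing when 25% or more of items are missing (3 of 10), even if the subject attends later. A subject whose infusion is stopped for an adverse event is withdrawn (Protocol 7.1), and early discontinuations complete the Visit 4 assessments (Protocol 1.3, note a). A later MADRS may then exist without a 24-hour one, and the SAP does not say whether it counts as Day 15. Day 8 is an outpatient visit, and Protocol 4.1 foresees missed follow-up visits.

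**Working it through.** **The plan's own figure.** The SAP states no figure for the imputation. The only related figure is the power statement in SAP III.C: "a sample size of 93 randomized subjects (31:31:31) will provide 80% power". Its inputs are a difference of 8 points for either dose against placebo, an SD of 11 and two-sided alpha 0.05.

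- SE of a difference = 11 × √(2/31) = 2.79.
- 8 / 2.79 = 2.86. Normal approximation: Φ(2.86 − 1.96) = 81.7%. Exact t with 60 df: 80.4%. The stated 80% reproduces.

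**Predictors of the 24-hour score, side by side.**

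| Source | MADRS timepoints used |
|---|---|
| SAP VII.E text and VAR statement | all six listed |
| FCS statement for ATPTN70 | predose, 2 h, 4 h |
| Primary MMRM, SAP VII.F | baseline and all post-baseline visits |

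Two of the five other timepoints are left out.

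**Information lost.** The documents give no between-visit correlations, so r = 0.4 to 0.8 is assumed under two patterns.

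- AR(1): earlier visits only, R² = r²; all visits, R² = 2r²/(1 + r²).
- Compound symmetry with k predictors: R² = k r²/(1 + (k − 1)r), with k = 3 (earlier only) or k = 5 (all).

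| r | AR(1) earlier → all (gain) | Compound symmetry earlier → all (gain) |
|---|---|---|
| 0.4 | 0.160 → 0.276 (0.12) | 0.267 → 0.308 (0.04) |
| 0.5 | 0.250 → 0.400 (0.15) | 0.375 → 0.417 (0.04) |
| 0.6 | 0.360 → 0.529 (0.17) | 0.491 → 0.529 (0.04) |
| 0.7 | 0.490 → 0.658 (0.17) | 0.612 → 0.645 (0.03) |
| 0.8 | 0.640 → 0.780 (0.14) | 0.738 → 0.762 (0.02) |

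For Day 8, adding Day 15 takes R² from 0.49 to 0.66 (AR(1), 0.7) or from 0.40 to 0.42 (compound symmetry, 0.5).

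**Effect on the 24-hour contrast.** Simulation with 31 per arm, SD 11 at each visit, true difference −8, 20 proper regression imputations, 24-hour ANCOVA on each completed dataset and 600 runs. Two mechanisms were assumed: missing completely at random, or placebo subjects missing at 24 hours only if their Day 8 score is more than 5.5 points above the mean, with random loss at the same rate in the active arms. Monte Carlo error of each mean is about 0.1; both methods were applied to the same datasets.

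| Missing, mechanism | Pattern | Earlier only | All visits | Gap |
|---|---|---|---|---|
| 5%, random | CS 0.5 | −7.97 | −7.96 | 0.01 |
| 5%, random | AR(1) 0.7 | −7.94 | −7.95 | 0.01 |
| 5%, Day 8-related | CS 0.5 | −8.01 | −8.09 | 0.08 |
| 5%, Day 8-related | AR(1) 0.7 | −7.58 | −7.83 | 0.25 |
| 10%, Day 8-related | CS 0.5 | −8.04 | −8.21 | 0.17 |
| 10%, Day 8-related | AR(1) 0.7 | −7.66 | −8.15 | 0.49 |

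With 5% missing at random, the mean pooled SE is 2.49 against 2.49 (CS) and 2.70 against 2.69 (AR(1)). The largest gap above is 0.49/2.79 = 0.18 SE.

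**Direction.** Here placebo subjects who do badly are lost, and earlier-only imputation shrinks the effect relative to all-visit imputation. Moving the loss to an active arm reverses the sign. A separate large-sample simulation (400,000 per arm, 5 to 10% of the active arm missing in relation to Day 8) gave −8.21 to −8.52 with earlier visits and −7.98 to −8.00 with all visits. Its two assumed correlation patterns gave later visits more weight (R² 0.34–0.45 rising to 0.62–0.68), so it is cited for the sign and not as a general size.

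**The case against.** The strongest reply has four parts.

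- **The text may allow a sequential scheme.** The sentence on variables agrees with the VAR statement, and its reference to each subsequent score can be read as visit-by-visit imputation, which the code carries out consistently. The code is also labelled an example. The reading is possible, but the words fully conditional tell against it. The example is the only place where predictor sets appear, and non-convergence is the only stated ground for changing them.
- **The affected cases should be few.** Subjects are in the clinic at 24 hours and missing data are expected to be infrequent. 5 to 10% of an arm of 31 is 2 or 3 subjects. For monotone dropout there is no later score to use. This stands, and it sets the priority.
- **A sensitivity analysis may use a different assumption from the primary.** True, and an all-visit imputation under MAR would largely reproduce the MMRM. But the SAP does not say that a narrower assumption is intended. Completer and treatment-compliant analyses are also planned, and MNAR analyses if more than 5% are missing at 24 hours (5 or more of 93).
- **The code does not discard the later scores altogether.** Also true: a reader might infer that Day 8 and Day 15 are ignored throughout, but they remain in the completed datasets and Day 15 is imputed from Day 8. The omission is in the imputation step, although once the 24-hour score is filled in they have almost no influence on the 24-hour contrast.

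**Conclusion.** The mismatch between the described method and the coded predictor lists is real, and it makes the imputation condition on less than the primary MMRM. It is minor. It reaches only the multiple-imputation analyses of the MADRS endpoints, and only subjects with a gap followed by an observed score. The shift in the 24-hour contrast is near zero under random loss and about 0.1 to 0.5 points if 5 to 10% are missing in relation to later scores, against an SE of about 2.8. These sizes rest on assumed correlations, missing rates and mechanisms; none is in the documents.

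Three stronger inferences are not supported:

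- That the primary result is biased: it uses no imputation.
- That the code would overstate the drug effect: the direction depends on which arm loses data.
- That any difference between the imputation and the MMRM must come from the code: the data could also produce one, and the point is only that the two causes could not be separated.

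The code sets a minimum of 0 and no maximum of 60. No effect of this has been shown, and it is not part of the case.

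**What to change.** In each FCS REG model, use treatment, region and all other MADRS timepoints as predictors, or drop the explicit effect lists so that the VAR-statement variables are used. The code then matches the text, and the imputation conditions on the same visits as the MMRM. If an earlier-visits-only scheme is intended, say so in SAP VII.E and give the reason.

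The cost is a few lines of code. SAP I.B allows changes until database lock, and the edit should be made before then so that it cannot look data-driven. Adding an upper bound of 60 is optional tidying.

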CADSS = Clinician-Administered Dissociative States Scale; CGI-I = Clinical Global Impression - Improvement; CGI-S = Clinical Global Impression - Severity; C-SSRS = Columbia Suicide Severity Rating Scale; CRF = case report form; DBP = diastolic blood pressure; 5D-ASC = 5-Dimensional Altered States of Consciousness Rating Scale; ECG = electrocardiogram; EQ-5D-3L = European Quality - 5 Dimensions - 3 Levels; EoI = End of Infusion; GAD-7 = Generalized Anxiety Disorder 7-Item Scale; HAM-D = Hamilton Depression Rating Scale; HIV = human immunodeficiency virus; MADRS = Montgomery Åsberg Depression Rating Scale; MGH-ATRQ = Massachusetts General Hospital Antidepressant Response Questionnaire; MINI = Mini-International Neuropsychiatric Interview; MOAA/S = Modified Observer's Assessment of Alertness/Sedation; OCBP = of childbearing potential; PK = pharmacokinetic; QIDS-SR-14 = Quick Inventory of Depressive Symptomatology – 14 Items; QIDS-SR-16 = Quick Inventory of Depressive Symptomatology – 16 Items; SBP = systolic blood pressure.

- a. Subjects who discontinue the study early will complete Visit 4 assessments and procedures as early termination procedures.
- b. All post-dose timepoints are relative to the start of infusion except for the 40-minute (EoI) timepoint. EoI procedures should occur 40 minutes after the start of infusion or at the end of infusion if the infusion continues beyond 40 minutes.
- c. Where activities at a given timepoint coincide, consideration should be given to ensure that the following order of activities is maintained: Efficacy rating scales (where more than one efficacy scale is assessed at a timepoint, the order of assessments should be MADRS, CGI-I and CGI-S, QIDS-SR-14/16, HAM-D, GAD-7 and EQ5D-3L); 12-lead ECGs; vital signs and pulse oximetry; safety rating scales (order: MOAA/S, CADSS and BPRS+); AE review, concomitant medication review, physical exam, and clinical laboratory assessment (including urine pregnancy test and drug/alcohol screen).
- d. Assessments and procedures should be started as close as possible after the EoI.
- e. Check eligibility.
- f. Assess clinical hematology and chemistry tests (non-fasting blood samples will be requested, but both fasting and non-fasting samples are acceptable).
- g. To be collected prior to clinical laboratory assessments. An ECG will be performed after 5 minutes in a supine position, if possible.

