7.0 DISCONTINUATION OF STUDY TREATMENT AND SUBJECT DISCONTINUATION/WITHDRAWAL

7.1 Discontinuation of Study Treatment

If an AE occurs during the administration of study treatment, discontinuation of the infusion may occur if the Investigator believes that it is in best interest of the subject. The subject will then be withdrawn from the study.

If a subject who does not meet the enrollment criteria is inadvertently administered study treatment, that subject may be discontinued from the study and the Sponsor or Sponsor designee must be contacted. An exception may be granted in rare circumstances for which there is a compelling reason to allow the subject to continue. In these rare cases, the Investigator must obtain documented approval from the Sponsor or Sponsor designee to allow the subject to continue in the study.

Subjects who discontinue study treatment will not be replaced.

See the Schedule of Activities ([Section 1.3](#)) for the data to be collected at the time of treatment discontinuation and follow-up and for any further evaluations that need to be completed.

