All reported study data will be recorded on the electronic case report forms (eCRF) using Medidata Rave EDC. During the data collection process, automated quality assurance programs will be used to identify missing data, out-of-range data, and other data inconsistencies.

B. Definition of Baseline

Unless otherwise indicated, the baseline is defined as the most recent non-missing and evaluable observation of the investigated parameter (including any unscheduled or repeat observations), prior to study drug dosing. Details are provided within the respective analysis sections of this SAP.

A change from baseline will be calculated as the post-baseline measurement minus the baseline measurement. If either the baseline or post-baseline value is missing, then the change from baseline value will be considered missing.

C. Missing Data

1. Primary and Secondary Endpoints

In general, the missing data which is observed from this study will be assumed to be missing-at-random (MAR).

Since subjects are confined to clinic at the time of the primary endpoint, it is anticipated that missing data will be infrequent. No imputation will be applied to primary analysis.

Baseline values will not be carried forward.

2. Imputation of Partial Dates

Partial dates are allowed in selected eCRFs including but not limited to AE onset and resolution dates, concomitant therapy start and stop dates, and medical history dates. An entry for the year is required in the eCRF system for each of these dates. Only the month and day may be entered as unknown. Dates from these forms will be reported in listings as collected. Every effort will be made to query missing dates.

A set of imputation rules will be implemented for the determination of whether an AE is treatment-emergent, or a therapy is concomitant. For the imputation methods of missing start or end dates in the classification of treatment-emergence or concomitant therapy, refer to [Section XI.A Missing or Partial Date Imputation](#).

D. Timing of Interim Analysis and Sample Size Reassessment

Not applicable.

E. Test Sizes

Statistical hypothesis testing will be performed based on the comparison of PCN-101 60 mg and 30 mg versus placebo, in two-sided tests with a significance level $\alpha=0.05$. The 95% of CI of the mean treatment difference will be two-sided.

F. Multiple Comparisons

No multiple comparison adjustments will be made for analyses.

G. Analysis Populations

Analysis sets are defined as described in [Table 2](#):

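### No planned missing-data analysis of the 24-hour MADRS departs from missing-at-random (MAR) unless missingness exceeds 5%, and that trigger has neither a denominator nor a method

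*SAP*

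**What the plan says.** - **Primary analysis (SAP VII.F).** An observed-case MMRM with no imputation. Missing data are taken as MAR and expected to be infrequent, because subjects are in clinic at 24 hours.
- **Multiple imputation (SAP VII.E and VII.G).** The SAP states that "sensitivity analysis exploring the MAR assumptions with multiple imputation of MADRS related endpoints will be performed". SAP VII.E describes the method as assuming MAR, with 50 imputations.
- **Refits (SAP VII.G and Table 3).** The same MMRM is run in treatment-compliant subjects only, and again in study completers only.
- **MNAR (SAP VII.E).** "If the missingness at the MADRS 24 hour timepoint is >5%, additional analyses exploring missing-not-at-random (MNAR) assumptions will be performed". No denominator or method follows.
- **Stated aim (SAP VII.A).** The sensitivity analyses are meant to vary the assumptions about missing data and the handling of intercurrent events.
- **Withdrawal (Protocol 7.1).** If the infusion is discontinued for an adverse event: "The subject will then be withdrawn from the study". Note a of the Schedule of Activities adds: "Subjects who discontinue the study early will complete Visit 4 assessments and procedures as early termination procedures".
- **Example code (SAP VII.E).** The VAR statement lists every timepoint, but the line for the fourth one, 24 hours, begins "FCS REG (ATPTN70 = TRTP REGION1 ATPTN20 ATPTN40 ATPTN50" and uses no later score.

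**The concern.** A sensitivity analysis for missing data is informative when it changes the assumption about the scores nobody saw. The analyses that run in all circumstances do not. MMRM and MI share MAR. SAP VIII.A counts an infusion shorter than 35 minutes as non-compliant, so the compliant refit drops a subject stopped before then, and the completer refit drops anyone withdrawn. A subject who stays in either refit with a missing 24-hour score is still handled under MAR.

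The primary estimand follows a treatment policy for incomplete infusions, so it wants the 24-hour score of a subject whose infusion was stopped. Protocol 7.1 withdraws that subject, and note a substitutes early-termination procedures, so the score may not be collected. Loss by this route could be related both to arm and to outcome.

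Whether an MNAR analysis then runs depends on a percentage with an undefined base. Two analysts could reach different decisions from the same data, and could do so after unblinding.

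**Working it through.** **Inputs.** SAP III.C: "a sample size of 93 randomized subjects (31:31:31) will provide 80% power to detect an 8-point difference", "assuming a common standard deviation (SD) of 11". SAP V.E: "in two-sided tests with a significance level" of 0.05. SAP VII.F words the test as one-sided at 0.025, which gives the same critical value in the favourable direction. The documents give no expected missing rate, and no figure for how far missing subjects might depart from MAR, so the shifts below are assumptions.

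**1. The plan's own figure.** SE = 11 × √(2/31) = 2.79. Two-sample t-test, 60 df, difference 8: power 80.4%. The stated 80% reproduces.

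**2. When the trigger fires** (all 93 treated and in the FAS, all missing subjects in one arm):

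| Missing | Overall, k/93 | >5%? | Per arm, k/31 | >5%? |
|---|---|---|---|---|
| 1 | 1.1% | no | 3.2% | no |
| 2 | 2.2% | no | 6.5% | yes |
| 4 | 4.3% | no | 12.9% | yes |
| 5 | 5.4% | yes | 16.1% | yes |

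The gap is therefore 1 to 4 missing subjects on the overall reading and 1 in an arm on the per-arm reading.

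**3. Bias for 4 missing in one active arm.** Bias = (4/31) × shift, where shift is how much worse the missing subjects' true mean change is than MAR implies. The observed numbers are 27 and 31, so SE = 11 × √(1/27 + 1/31) = 2.90. With 56 df the critical difference is 2.003 × 2.90 = 5.80. Covariate and repeated-measures gains are ignored.

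| Assumed shift | Bias (points) | Share of 8-point target | Favourable-tail error (nominal 0.025) |
|---|---|---|---|
| 5 | 0.65 | 8% | 0.041 |
| 8 | 1.03 | 13% | 0.054 |
| 10 | 1.29 | 16% | 0.064 |

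**4. Shift at which significance is lost.** Tipping shift = (observed difference − 5.80) × 31/4:

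- observed 6.5: 0.70 × 7.75 = 5.4 points
- observed 7.0: 1.20 × 7.75 = 9.3 points
- observed 8.0: 2.20 × 7.75 = 17.0 points (about 17)

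**5. Information used at 24 hours.** The MMRM with unstructured covariance draws on all visits, including Day 8 and Day 15. The example imputation line for the 24-hour score uses arm, region, predose, 2-hour and 4-hour scores only. For a subject who misses 24 hours but returns later, the MI uses less information than the analysis it is meant to check.

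**The case against.** The strongest reply is that little will be missing. Subjects are in clinic at 24 hours, this is a Phase 2a proof-of-concept study, and a threshold for MNAR work is a defensible economy. The worked case also puts all 4 losses in one arm. Split 2 and 2 across the active arms, the bias per comparison is (2/31) × 5 to 10 = 0.32 to 0.65 points. All of this stands, and it is why the effect is called modest. It does not supply the missing denominator or method.

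Four stronger readings are tempting, and the documents do not support them.

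- *The trigger is pooled.* SAP VII.E names no arm but does not say overall either. Per arm, 2 of 31 would fire it.
- *Informative loss in one arm is never tested.* On either reading, 5 or more missing in one arm triggers MNAR work.
- *Loss is expected mainly in the active arms.* Protocol 2.3 and 4.3 report fewer effects at 30 and 60 mg than at 100 and 150 mg, so dose-related loss is plausible. No rate of stopped infusions is given, and Protocol 7.1 says only that stopping may occur.
- *Missing subjects are imputed as if they did as well as everyone else in their arm.* The model conditions on the predose, 2-hour and 4-hour scores, so poor early scores carry through.

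Nor does note a mean that early-termination ratings are analysed as Visit 4 data. It says which procedures to perform and sets no analysis mapping.

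The imputation code is labelled an example, and later scores add little for a subject withdrawn on Day 1. That change is a MAR refinement, separate from the MNAR gap.

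**Conclusion.** The point holds in limited form. Every unconditional analysis of the 24-hour MADRS either assumes MAR or drops subjects who stopped early and were withdrawn. The only departure from MAR depends on a trigger with no stated base or method, which falls short of the aim in SAP VII.A. Between 1 and 4 missing subjects (overall reading), or 1 in an arm (per-arm reading), would go unchecked.

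At assumed shifts of 5 to 10 points, 4 such subjects in one active arm bias the difference by 0.65 to 1.29 points, or 22% to 45% of the standard error of 2.90. A borderline result is exposed; a clear one is not. If missingness is as low as the plan expects, the impact is smaller still. One group lies outside the calculation: treated subjects with no postbaseline assessment leave the FAS (SAP V.G), so on an FAS denominator they would not count toward the 5%.

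**What to change.** In SAP VII.E and VII.G:

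1. Remove the 5% trigger. Whenever any 24-hour MADRS score is missing, run one delta-adjusted tipping-point analysis, worsening the imputed active-arm scores in steps until the conclusion changes. The planned 50-imputation PROC MI step can do this with its MNAR statement. Control-based imputation from the placebo arm is an optional addition.
2. Report 24-hour missingness by arm, including treated subjects excluded from the FAS for having no postbaseline assessment. An FAS-based tipping-point analysis does not reach that group, so its size must be visible.
3. Let the imputation model for the 24-hour score (ATPTN70) also condition on the Day 8 and Day 15 scores, so that it uses the information the MMRM uses.

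The cost is SAP wording, a few hours of programming and one more sensitivity table. No new data are needed, and SAP I.B allows changes until database lock.
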